## **XI. SAMPLE SIZE**

This will be a pilot study and therefore 10 subjects in each arm, for a total of 20 subjects, will allow us to determine if the therapy is effective. To allow for screen failures, 45 subjects are planned for screening.

## **XII. DATA ANALYSIS**

- A. The primary outcome measure will be:
  - 1. change in penile curvature, as measured by a protractor from pictures taken at baseline versus the end of treatment at 16 weeks
- B. Secondary outcomes will be measured objectively and subjectively.
- C. Objective measures will be:
  - 1. improvements in penile blood flow
  - 2. reduction in penile plaque size as seen on ultrasound
- D. Subjective measures will be:

1. changes in IIEF scores

As mentioned above, these objective and subjective measurements will be performed before and after the 16 week treatment.

Data will be analyzed using a t-test to compare differences between the two groups.

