## V. DESIGN

This is a randomized, placebo-controlled, cross-over, single-center trial. Study drug is Botulinum toxin type A (BOTOX®). Subjects who meet the inclusion criteria for the study will be randomized to either the treatment or placebo arm.

**ARM 1 - Treatment:** Injection solution will consist of 100 units of BOTOX® in 10 cc of preservative free normal saline, or

**ARM 2 - Placebo:** Injection solution will consist of 10 cc preservative free normal saline.

The Week 16 Visit will be the end of the study participation for those subjects in Arm 1 and who did not develop ED (as defined as a drop in IIEF scores of more than 4 points from Baseline IIEF score). The Week 16 Visit will be the end of study participation for subjects in Arm 2 and who developed ED. For subjects in Arm 2, crossover to BOTOX treatment will begin after the Week 16 Visit by repeating the study schedule as for Week 0 to Week 16. Continuation visits at Months 6, 9, and 12 will occur for subjects in Arm 1 and who developed ED.

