## VI. RANDOMIZATION PROCEDURES:

The subjects will be randomized to the arms as they are enrolled and meet eligibility criteria. The odd number (1, 3, 5...) of subjects will be in ARM 1 and even numbers (2, 4, 6...) of subjects will be in the ARM 2. The randomization scheme will not result in selection bias.

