## VIII. PROCEDURES

Subjects who meet the inclusion criteria for the study will be randomized to either the treatment or placebo arm. Prior to treatment, all subjects will have a penile injection with Caverject 20mcg/cc to induce a penile erection. During the erect state, penile curvature will be assessed, pictures will be taken for later measurement of penile curvature, and ultrasound will be used to assess penile blood flow and plaque size. A penile duplex with intercavernosal injections of a vasoactive substance is part of our standard care for Peyronies disease diagnosis. Subjects will also be asked to complete the International Index of Erectile Function (IIEF) questionnaire.

Injections will be performed using our standard protocol currently used for verapamil injections, but instead we will be using 100 units of BTX-A in 10cc of preservative free normal saline, or 10cc of preservative free normal saline for placebo and plaque breakdown injections. The standard injection procedure consists of the following:

1. Subjects will be explained the risks and benefits of the procedure and will give informed consent.
2. Blood pressure, pulse, and oxygen saturation will be monitored throughout the procedure.
3. A penile block with 10cc of lidocaine without epinephrine will be given, followed by an observation period of 10 minutes to assure no immediate adverse reaction to lidocaine.
4. Approximately 20 to 30 injections with a 20 gage needle will be given directly into the penile plaque. The skin will not be punctured with each injection, but the needle will move within the plaque. Injection solution will consist of 100 units of BTX-A in 10 cc of preservative free normal saline, or 10 cc of preservative free normal saline.
5. Subjects in the placebo arm will only receive 10 cc of preservative free normal saline.
6. Subjects will be monitored for 1 hour after the procedure to ensure that their vital signs are stable and that there are no signs of penile hematoma.
7. Safety will be assessed by following the subject closely for one hour after the procedure.
8. Subjects will be given strict instructions to call and return to the clinic or the ER for any adverse side effects.

Subjects randomized to ARM 1 will receive one injection of 10 cc preservative normal saline at study start (week 0), followed by 100 U Botox in 10cc saline at visit two (week 4), then saline injections at weeks 8 and 12, thus a total of 4 injections (1 saline, 1 Botox, 2 saline).

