#### **B. Protocol Monitoring:**

The PI will be responsible of monitoring the safety and efficacy of the trial, executing the Safety Monitoring Plan, and complying with the reporting requirements. Monitoring will be performed on a regular basis. All clinical and safety data including AE's, toxicities, and responses will be reviewed by the PI, investigators and research staff at regularly scheduled research meetings. The PI will provide a summary of the Safety Monitoring Plan findings to the appropriate regulatory authorities on an annual basis as part of the progress report. The progress report will include participant demographics, expected versus actual recruitment rates, summary of AEs and SAEs, any QA or regulatory issues that occurred during the past year, and any actions or changes with respect to the protocol.

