## **XVIII. CONFIDENTIALITY**

Each subject will be assigned a unique, consecutive three-digit identification number (i.e., 001, 002, ...). The study number will be utilized for identification of the subject throughout the study. The clinical study coordinator of the trial will maintain the code that links the name of the participant to their study ID number. The study coordinator will maintain the code in a secured cabinet and the code will be kept confidential. Only the clinical study coordinator and PI can access and view the codes.

The research records will be maintained in the Scott Department of Urology. The computers used for this study are password protected. The data will be kept by the clinical coordinator in a secure locked area. Areas are protected after hours by an electronic door locking systems. The Scott Department of Urology adheres to the HIPAA guidelines.

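### Nothing in the plan masks the reader of the primary-endpoint photographs to arm or visit, and odd/even allocation reveals the arm to any reader who has the enrolment order

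*Combined protocol and SAP*

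**What the plan says.** Section XII names one primary outcome: "change in penile curvature, as measured by a protractor from pictures taken at baseline versus the end of treatment at 16 weeks". Section VIII places the reading after the visit: "pictures will be taken for later measurement of penile curvature". The groups are then compared by t-test.

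Neither section says who holds the protractor, how the photographs are labelled, or whether the reader is masked to arm or to visit. Section V describes the design without any blinding term. The only mention of blinding in the available text is in Section I, and it concerns a cited study of facial wounds.

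Section VI sets allocation by order of enrolment: "The odd number (1, 3, 5...) of subjects will be in ARM 1", with even numbers going to Arm 2. The restricted code in Section XVIII ("Only the clinical study coordinator and PI can access and view the codes") links names to study numbers. It is not described as a treatment code.

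Both arms receive 10 cc injections at Weeks 0, 4, 8 and 12 (Section VIII). This may keep subjects unaware of their arm, but it does nothing for a staff member reading photographs.

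**The concern.** Placing a protractor on a photograph involves choosing the axes of the shaft, so two careful readers can differ by some degrees. If the reader knows which arm a subject is in and which photograph is the later one, expectation can shift the reading. With alternating allocation there is no sealed code to break: the enrolment order is the allocation list.

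Two things are at stake. Section XI says that the 20 subjects will show whether the therapy works. Section VIII makes the placebo arm's crossover option depend on a significant improvement over placebo. If the reading has leaned, re-analysing the recorded angles cannot remove the lean.

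**Working it through.** **Plan's own figure.** There is none to reproduce. Section XI gives 10 per arm without alpha, power, effect size or SD.

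**Which lean matters.** Let L(g,v) be the average reading error in arm g at visit v (0 = baseline, 16 = Week 16). The bias in the between-arm difference in mean change is

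b = [L(1,16) − L(1,0)] − [L(2,16) − L(2,0)].

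If the reader leans equally on a subject's two photographs, L(g,16) = L(g,0) in each arm and b = 0. If the reader leans on Week 16 photographs equally in both arms, b = 0 again. Only a lean that depends on arm and visit together survives. Masking therefore has to cover both.

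**Inputs.**
- 10 per arm (Section XI) and a t-test between groups (Section XII).
- Assumed, because the plan gives none of them: two-sided 5% level; SD of the change of 10, 15 or 20 degrees; differential lean b of 1 to 5 degrees; no true effect; a reader who knows every arm and visit.

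**Formula.** With df = 18 the critical value is 2.101. The noncentrality is (b/SD) × √(10/2) = (b/SD) × 2.236. The false-positive rate is the probability that a noncentral t with 18 df exceeds 2.101 in absolute value.

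Example: b = 3 and SD = 10 give 0.3 × 2.236 = 0.671 and a rate of 9.7%. For b = 5 and SD = 10 the noncentrality is 0.5 × 2.236 = 1.118 and the rate is 18.5%.

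| Lean b in the change (degrees) | SD 10 | SD 15 | SD 20 |
|---|---|---|---|
| 0 | 5.0% | 5.0% | 5.0% |
| 1 | 5.5% | 5.2% | 5.1% |
| 2 | 7.1% | 5.9% | 5.5% |
| 3 | 9.7% | 7.1% | 6.2% |
| 5 | 18.5% | 10.9% | 8.3% |

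Simulation agrees with these values to within about 0.1 percentage point. The rate reaches 10% at a lean of 3.1, 4.6 or 6.2 degrees for the three SDs.

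If each subject's arm is known with probability one half, simulation gives about 6.2%, 5.6% and 5.3% for 3 degrees, and 8.3%, 6.5% and 5.8% for 5 degrees.

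**The case against.** The strongest reply is that the documents show a silence, not an unmasked reader. That stands. The text does not say that the reader will know any subject's arm, and the removed front matter could carry a general blinding label. Such a label would still not set a procedure for reading photographs, and the sections where that procedure belongs are available.

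A second reply is that the damage can be undone. This stands in part. Appendix II (2.1.4.6) requires source documents for the case report form data at audit. If the photographs are kept, a masked re-reading after the trial could replace a suspect one.

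A reader might infer more than the documents support:
- *That the study number gives away the arm.* Section XVIII says "Each subject will be assigned a unique, consecutive three-digit identification number", but not that it follows enrolment order. Section XI says "To allow for screen failures, 45 subjects are planned for screening" against 20 places, so numbers given at screening need not match the odd/even sequence.
- *That the Week 16 pathways reveal the arm.* This needs reading to come after those pathways diverge, and knowledge of erectile dysfunction status as well. If crossover waits for a significant curvature result, reading must come first.
- *That staff meetings show curvature by arm.* Section XIII.B says "responses will be reviewed by the PI, investigators and research staff at regularly scheduled research meetings", but this is general departmental wording. Nothing shows that protractor readings or by-arm results are presented. The same section makes the PI responsible for monitoring efficacy, so a rewrite there is not proposed.
- *That any arm-related lean biases the result.* It does not; a lean common to both visits cancels in the change.

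**Conclusion.** The point holds as a gap in the plan: the sole primary endpoint has no masked reading specified, and a reader who has the enrolment order would know the arm. Confidence is high for the absence of masking text only. It does not extend to the reader's knowledge of the arm or to the size of any bias.

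The size is hypothetical. Differential leans of 1 to 2 degrees do little harm in most of the settings examined, 3 degrees can nearly double the nominal error at the smallest SD, and 5 degrees is material at SDs of 10 and 15. These figures rest on the assumed SDs, leans and test level, and on a fully informed reader. They describe a lean in the change score, not general reader error. This is a cheap improvement, not evidence that the result will be wrong.

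**What to change.** Add to Sections VIII and XII:
1. Baseline and randomized-period Week 16 photographs are relabelled with random codes that hide subject number, enrolment number, arm and visit, and are shuffled.
2. They are read in one batch after the last randomized-period Week 16 visit, by existing staff without access to the key and, where possible, not by the person who injected or photographed.
3. The coordinator holds the key, and the readings are locked before it is opened.

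**Cost.** About 40 photograph sets to recode (20 subjects × 2 visits), and no subject-by-subject protractor readings before the lock. The group t-test already has to wait for the last Week 16 visit. The Week 16 erectile dysfunction rule uses IIEF scores, so it is unaffected.

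**Limits.** This does not mask the person who takes the photograph. It does not cure alternating allocation, which is a separate issue.

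**To reconcile.** Section V says "For subjects in Arm 2, crossover to BOTOX treatment will begin after the Week 16 Visit", and the third footnote in Section VII agrees. Section VIII instead offers crossover only if the 16-week comparison is significant. These texts must be reconciled with each other and with the timing of the batch reading.

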There are two phases of Peyronie's disease: the active phase and the quiescent phase. The active phase usually occurs during the first 12 months of the disease and is associated with constant changing of the plaque and penile pain. Surgery is contraindicated during the active phase and is usually indicated after 18 months from the onset of the disease, when the plaque has stabilized. The stabilization of the plaque is known as the quiescent phase. During the active phase, approximately 15-20% of patients can get spontaneous resolution of their disease. Therefore, injections initiated during the active phase are also discouraged by some because this may lead to further trauma as opposed to allowing for spontaneous resolution.

*Hypothesis:* BTX-A penile injections into Peyronie's plaques can significantly prevent scar formation and promote scar breakdown as evidenced by reduced penile curvature.

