## **II. PURPOSE**

The purpose of this study is to establish the efficacy of botulinum toxin in treating Peyronie's disease.

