## **X. CRITERIA FOR DISCONTINUING THE STUDY**

- A. Subjects unable to tolerate BTX-A due to side effects.
- B. Subjects can request removal from the study for any reason at any time.
- C. Subjects may be withdrawn at any time at the discretion of the investigator for safety, compliance, or other reasons.

A discontinuation occurs when an enrolled subject ceases participation in the study, regardless of the circumstances, prior to completing the protocol.

The reasons for a subject discontinuing from the study will be recorded in the Case Report Form.

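### Sections XI and II promise an efficacy answer from 10 subjects per arm, a size with 80% power only for differences of about 1.3 SD of change or larger; as a secondary point, the t-test leaves baseline curvature unused as a covariate

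*Combined protocol and SAP*

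**What the plan says.** Section XI (Sample Size) reasons: "This will be a pilot study and therefore 10 subjects in each arm", 20 in all, "will allow us to determine if the therapy is effective". It adds: "To allow for screen failures, 45 subjects are planned for screening". Section II (Purpose) says: "The purpose of this study is to establish the efficacy of botulinum toxin". The hypothesis at the end of Section I is that the injections "can significantly prevent scar formation and promote scar breakdown as evidenced by reduced penile curvature".

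Section XII (Data Analysis) defines the primary outcome as "change in penile curvature, as measured by a protractor from pictures taken at baseline versus the end of treatment at 16 weeks" and gives one sentence on method: "Data will be analyzed using a t-test to compare differences between the two groups". That the test is applied to change follows from the outcome definition; the sentence itself names no variable and no covariate. Sections VII and VIII have curvature measured before treatment in all subjects.

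Section X foresees losses after enrolment: "Subjects can request removal from the study for any reason at any time". No alpha, sidedness, power, target difference, SD or dropout allowance appears anywhere.

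**The concern.** A pilot label can justify a small sample. It cannot justify a statement that the sample will settle whether the treatment works, and here the label is the only support offered. The plan does not say how a non-significant result will be read, so a null result could be reported as a finding that the treatment does not work when the trial had little chance of detecting a moderate effect.

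The secondary matter is efficiency. With so few subjects, precision is scarce. Baseline curvature is already collected, yet it enters the analysis only by subtraction.

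**Working it through.** **Inputs from the plan.** 10 per arm, 1:1 (Section XI); outcome is change in curvature from baseline to Week 16, two-group t-test (Section XII).

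**Assumed, because the plan is silent.** Two-sided alpha 0.05, with one-sided 0.05 as a variant; 80% power; 10, 9 or 8 evaluable per arm. Differences are in units of the SD of change, since no SD in degrees is given.

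**The plan's own figure.** The 10 per arm cannot be reproduced, because no inputs are attached to it. The calculation is therefore inverted: what can 10 per arm detect?

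**Power of the t-test.** With n per arm and a true difference of d SD, the statistic is noncentral t with 2n − 2 degrees of freedom and noncentrality d × √(n/2). The 95% CI half-width is t(0.975, 2n − 2) × √(2/n); for n = 10 this is 2.101 × √0.2 = 0.94 SD.

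| Evaluable per arm | 80% power at | Power at 1.0 SD | Power at 0.8 SD | Power at 0.5 SD | CI half-width |
|---|---|---|---|---|---|
| 10 | 1.325 SD | 56% | 39.5% | 18.5% | 0.94 SD |
| 9 | 1.41 SD | 51% | 36% | 17% | 1.00 SD |
| 8 | 1.51 SD | 46% | 32% | 15% | 1.07 SD |

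At one-sided 5% with 10 per arm, 80% power is reached at 1.16 SD. At two-sided 5%, 80% power would need 17, 26 or 64 evaluable per arm for 1.0, 0.8 or 0.5 SD.

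**What a result could show.** With 10 per arm, an observed difference above about 0.94 SD excludes zero. An observed 0.5 SD gives 0.5 ± 0.94, that is −0.44 to 1.44 SD. Even an observed difference of zero leaves an upper limit of 0.94 SD. So a non-significant result with an observed difference of zero or better cannot rule out a large benefit.

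**Secondary point: ANCOVA against the t-test on change.** Let ρ be the baseline to Week 16 correlation and k the Week 16 SD divided by the baseline SD. The documents give neither, so both are assumed ranges.

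- Variance ratio before the cost of estimating the slope: k²(1 − ρ²) / (1 + k² − 2ρk). It never exceeds 1 and equals 1 when k = 1/ρ.
- Average cost of estimating the slope: 1 + 1/(N − 4) = 1 + 1/16 = 1.0625 with N = 20.
- Example at k = 1, ρ = 0.3: (0.91/1.40) × 1.0625 = 0.691, or −31%.
- Example at k = 1, ρ = 0.9: (0.19/0.20) × 1.0625 = 1.009, or +1%.

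Average change in variance with ANCOVA, 10 per arm:

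| k | ρ = 0.3 | 0.5 | 0.7 | 0.8 | 0.9 |
|---|---|---|---|---|---|
| 0.8 | −47% | −39% | −33% | −32% | −35% |
| 1.0 | −31% | −20% | −10% | −4% | +1% |
| 1.11 | −24% | −12% | −2% | +3% | +6% |

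The 1.0625 is an average over chance baseline imbalance. In one trial the factor is 1 + t²/18, where t is the two-sample t statistic for baseline curvature. With normal baselines and random allocation it exceeds 1.0625 in about 30% of trials and 1.245 in about 5% (t = 2.101 gives 1 + 4.414/18 = 1.245).

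With 17 degrees of freedom and the average variance ratios above, ANCOVA reaches 80% power at 1.11 to 1.34 SD of change with equal SDs. Over the whole grid the range is about 0.97 to 1.37 SD.

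**The case against.** **It is a pilot, and pilots need no power calculation.** This stands as a defence of the sample size: nothing here shows that 20 subjects is wrong for a pilot. It does not defend the inference in Section XI or the purpose in Section II.

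**Alpha is assumed, and the Section I hypothesis is directional.** Fair, so the one-sided figure is given. At 1.16 SD the conclusion is unchanged.

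**A reader might infer that the trial cannot determine anything.** The documents and figures do not support that. An observed difference above about 0.94 SD would exclude zero, and power is good if the true effect is very large. The shortfall is for moderate effects and in the reading of a null result.

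**A reader might infer that the t-test is an error.** It is not. A t-test on change is valid under proper randomization, and the case for ANCOVA rests on a correlation and an SD ratio that the plan does not give. The eligibility criteria require stable disease, which may make the correlation high; at 0.8 to 0.9 with equal SDs the average gain is 4% or nothing. Nor is the possible loss capped at 6%: that is an average, and a single trial with unlucky baseline imbalance can lose more.

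**Conclusion.** The main point holds. Sections XI and II claim a property that the design has only for very large effects: 80% power at about 1.3 SD of change or larger, if alpha is two-sided 5% and all 20 subjects are evaluable. That figure rises to about 1.4 and 1.5 SD with 9 and 8 per arm. It cannot be turned into degrees without an SD of curvature change, which the plan does not give.

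The secondary point is an inexpensive improvement to Section XII, of uncertain size. ANCOVA does not make the efficacy claim true, and neither it nor the t-test corrects any bias from the odd/even allocation in Section VI. The differing statements on when cross-over starts are a separate matter and form no part of this point.

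**What to change.** 1. **Section XI.** Replace the claim with wording such as: 'Ten subjects per arm is a pilot size. Assuming a two-sided 5% test, an unadjusted comparison of change scores has 80% power for differences of about 1.3 SD of change or larger if all 20 subjects are evaluable, and of about 1.4 or 1.5 SD or larger with 9 or 8 evaluable per arm. The arm difference will be estimated with a 95% CI. A non-significant result will not be read as lack of effect.' If the investigators intend another alpha or a one-sided test, they should name it and restate the figures.
2. **Section II.** Align the purpose with this, for example: 'to estimate the effect of botulinum toxin on penile curvature in a pilot study'.
3. **Section XII (advisable, not a correction).** Analyse Week 16 curvature, or change, by ANCOVA with arm and baseline curvature; both give the same adjusted arm difference. Report it with its 95% CI.

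Cost: a few sentences and a more modest claim, with no extra subjects, visits or data. ANCOVA uses one degree of freedom (17 instead of 18). With 20 subjects it costs on average up to about 6% of variance when the correlation brings no gain, and possibly more in a single trial with marked baseline imbalance.

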#### **IV. ELIGIBILITY CRITERIA**

##### **A. Inclusion:**

1. Subjects with stable Peyronie's plaques.
2. Males at least 18 years of age
3. Prior history of failed penile injection therapies is allowed.
4. Must give informed consent.

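### The only planned analysis is a t-test on change in curvature; adjusting for baseline curvature by ANCOVA would guard against chance imbalance with 10 per arm at little cost

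*Combined protocol and SAP*

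**What the plan says.** Section XII (Data Analysis) defines the primary outcome as "change in penile curvature, as measured by a protractor from pictures taken at baseline versus the end of treatment at 16 weeks" and names one method for all outcomes: "Data will be analyzed using a t-test to compare differences between the two groups". That the test is applied to change follows from the outcome definition; the sentence itself does not say so. No covariate, regression model, confidence interval or sensitivity analysis is mentioned anywhere.

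The baseline value is already collected. Section VIII (Procedures) has all subjects examined before treatment: "During the erect state, penile curvature will be assessed, pictures will be taken for later measurement of penile curvature". The Schedule of Events marks the curvature assessment and photographs at Baseline and at Week 16.

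Section XI (Sample Size) plans "10 subjects in each arm, for a total of 20 subjects" and gives no alpha, power, SD or effect size. Section VI (Randomization Procedures) allocates by enrolment number: "The odd number (1, 3, 5...) of subjects will be in ARM 1 and even numbers" to Arm 2. There is no stratification by curvature.

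**The concern.** In a trial of 20, the arms can easily start with visibly different mean curvature. A change score does subtract baseline, but with a coefficient fixed at 1. If the true slope of Week 16 curvature on baseline is below 1, the arm that starts higher tends to show the larger fall even without a treatment effect. Averaged over many trials this cancels, but the one trial that is run cannot average it away. Readers facing unequal baselines would have no prespecified way to say how much of the difference in change they explain.

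The result carries weight. Section XI claims that the sample "10 subjects in each arm, for a total of 20 subjects, will allow us to determine if the therapy is effective", and Section VIII makes the crossover offer to placebo subjects depend on a significant benefit over placebo at 16 weeks.

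**Working it through.** **Inputs from the documents.** n = 10 per arm, 1:1; outcome is change from baseline to Week 16; two-group t-test.

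**Assumptions, because the documents give no figure.** Two-sided alpha 0.05; allocation that behaves as random; bivariate normal curvature; correlation ρ between baseline and Week 16 shown over a range; equal SDs at the two visits, relaxed in step 5. Eight completers per arm is an illustrative dropout case. The stated sample size has no inputs behind it and so cannot be reproduced.

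**1. How often are the arms imbalanced?** The baseline mean difference has SD √(2/n) = √0.2 = 0.447 baseline SDs.
- 10 per arm: P(|difference| > 0.5 SD) = 2 × [1 − Φ(0.5/0.447)] = 0.264.
- 8 per arm: 2 × [1 − Φ(0.5/0.5)] = 0.317.

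**2. How far does the change score move?** The shift has size (1 − ρ) × imbalance. The standard error of the difference in change is √(2(1 − ρ) × 0.2) SD. For an imbalance of 0.5 SD:

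| ρ | Shift (SD) | SE (SD) | Shift/SE |
|---|---|---|---|
| 0.5 | 0.25 | 0.447 | 0.56 |
| 0.7 | 0.15 | 0.346 | 0.43 |
| 0.9 | 0.05 | 0.200 | 0.25 |

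**3. False-positive rate with no true effect** (one million simulated trials per setting). Both methods reject in about 5% of all trials. Split by baseline imbalance, the t-test behaves as follows:

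| ρ | t-test, imbalance > 0.5 SD | t-test, imbalance ≤ 0.5 SD |
|---|---|---|
| 0.5 | 9.5% | 3.4% |
| 0.7 | 7.8% | 4.0% |
| 0.9 | 5.9% | 4.7% |

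ANCOVA rejects in about 5% in every cell.

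**4. Precision and power.** var(ANCOVA)/var(change) = [1 + 1/(2n − 4)] × (1 + ρ)/2. At n = 10 the first factor is 1 + 1/16 = 1.0625. Power is simulated at an effect of 1.325 SDs of change, where the t-test with 18 df has 80% power.

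| ρ | Variance ratio | ANCOVA power |
|---|---|---|
| 0.3 | 0.69 | 92% |
| 0.5 | 0.80 | 88% |
| 0.7 | 0.90 | 84% |
| 0.8 | 0.96 | 82% |
| 0.9 | 1.01 | 79% |
| 0.95 | 1.04 | 78% |

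Break-even on variance is ρ = 2/1.0625 − 1 = 0.88. On confidence interval width, with the critical t rising from 2.101 (18 df) to 2.110 (17 df), it is 0.87. With 8 completers per arm the factor is 1 + 1/12 = 1.0833, and break-even falls to 0.85 on variance and 0.82 on width.

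**5. Unequal SDs.** Let r = Week 16 SD / baseline SD. The variance ratio is then 1.0625 × r²(1 − ρ²) / (1 + r² − 2ρr).
- r = 1.2: the ratio is 1.03 at ρ = 0.7 and 1.06 at ρ = 0.8; ANCOVA power is 79% and 78%. Break-even falls to about ρ = 0.64.
- r = 0.8, ρ = 0.8: the ratio is 0.68 and power is 92%.

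Because 1 + r² − 2ρr = r²(1 − ρ²) + (1 − ρr)², the ratio can never exceed 1.0625 at n = 10, whatever r and ρ are.

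**The case against.** The strongest reply is that nothing here is wrong. The t-test on change is unbiased and holds its 5% level under random allocation, so this is a choice between two valid estimators. That stands, and it is why the point is optional.

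Second, the trial enrols "Subjects with stable Peyronie's plaques", and Section I says that "The stabilization of the plaque is known as the quiescent phase". Stable disease makes a high correlation plausible, and then the benefit nearly disappears. At ρ = 0.9 the shift is only 0.05 SD, and in trials with imbalance above 0.5 SD ANCOVA has about 75% power against 79% for the t-test. This also stands, but a high correlation is not established. Protractor readings from photographs of two separately induced erections carry measurement error, which lowers it.

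Third, the break-even near 0.87 to 0.88 depends on equal SDs. That is correct: a Week 16 SD 20% larger moves it to about 0.64. The loss stays bounded at about 6% in variance (about 2.5 power points in the cases run with 10 per arm), while the gains reach 12 points or more.

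Fourth, odd/even allocation is predictable, so imbalance need not be due to chance, and adjusting for one measured covariate does not cure that. This is right. Allocation and sample size are the larger problems: 10 per arm gives 80% power only for about 1.32 SDs of change, and ANCOVA does not make that adequate.

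**Conclusion.** The concern holds, as an improvement that could be made and not as an error. The plan collects baseline curvature in everyone and leaves it out of the analysis model. About one trial in four of this size would have a baseline imbalance above 0.5 SD. In those trials, with equal SDs, the t-test's false-positive rate is roughly 6% to 9.5% for correlations from 0.9 down to 0.5, against 5% for ANCOVA.

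Protection against the imbalance that actually occurs is the main reason to change; precision is secondary and could go either way. The size rests on allocation behaving as random, a linear common slope, approximate normality, and assumed values for the correlation and SDs.

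**What to change.** For the primary outcome, replace the t-test sentence in Section XII with:

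> Week 16 curvature will be compared between arms by ANCOVA with arm as factor and baseline curvature as covariate, reporting the adjusted difference and its 95% confidence interval. An unadjusted t-test on change from baseline will be a sensitivity analysis.

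Secondary outcomes may be handled the same way, each with its own baseline; no gain has been calculated for them.

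The change needs no new subjects, visits or measurements, but must be fixed before outcome data are seen. It uses one residual degree of freedom (18 to 17) and inflates variance by about 6% for estimating the slope. With equal SDs, the loss at ρ = 0.95 is about 2 power points (about 2.5 with 8 completers per arm). The odd/even allocation in Section VI needs its own correction.
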